13.8.2.2. Primary Safety Endpoint

The primary safety endpoint is 1-year incidence of major stroke in the territory supplied by the treated artery or neurological death. The incidence will be summarized using counts and percentages; the 1-sided

PR-NV16099	Version C	Page 113 of 144		Medtronic
------------	-----------	-----------------	--	-----------

upper bound of the 97.5% confidence limit for the incidence will be evaluated relative to the a priori safety threshold of 14%. Given the primary safety endpoint reported in PMA P100018 was 5.6%, an incidence of ≤7% for the primary safety endpoint would be considered clinically acceptable within the confines of a study of this general size. The hypothesis for evaluating the primary safety endpoint will be evaluated according to the following 2 requirements:

Requirement 1: The incidence of primary safety events must be \leq 7%, and

Requirement 2: The null hypothesis must be rejected in favor of the alternative:

 H_{o} : Incidence at 1-year post-procedure of major stroke and/or neurological death is \geq 14.0%

 H_a : Incidence at 1-year post-procedure of major stroke and/or neurological death is < 14.0%

If the incidence of primary safety events is ≤7% and the upper bound of the 1-sided 97.5% exact binomial confidence interval is <14%, the primary safety endpoint will have been met.

All eligible patients will undergo follow-up at 12 months.

13.8.3. Secondary Endpoint Analysis

All the secondary endpoints will be summarized using frequency tables presenting counts and percentages; no statistical testing will be performed against any preset thresholds for the secondary endpoints. The secondary endpoints include the following:

The following will be assessed for the effectiveness outcome measures:

- 1. Incidence of successful device implantation at the target site
- 2. Incidence of complete aneurysm occlusion (Raymond Roy Class 1) at 1- and 3-years postprocedure
- 3. Incidence of target aneurysm recurrence at 1- and 3-years post-procedure

The following will be assessed for the secondary safety endpoints:

- Incidence of major stroke in the territory supplied by the treated artery or neurological death at 2- and 3-years post-procedure
- 2. Incidence of major stroke in the territory supplied by the treated artery or neurological death at 30 days post-procedure
- Incidence of delayed intraparenchymal hemorrhage >30 days post-procedure through 1-year post-procedure

ADVANCE Clinical Investigation Plan			
PR-NV16099	Version C	Page 114 of 144	Medtronic

Incidence of subjects with disabling strokes that have a mRS decline to a score of 3 or more (mRS ≥ 3) due to a stroke-related cause assessed at a minimum of 90 days post-stroke event at 1 year, 2 year, and 3 year post-procedure

13.8.4. Adverse Events

Adverse events will be coded according to the Medical Dictionary for Regulatory Activity (MedDRA) system dictionary.

CEC adjudicated data Tables to summarize the incidence rates will be created for each of the following groups: (At 1 year, 1- 2 years, and 2- 3 years)

- Adverse events (non-Serious) related to intervention (Procedure, anti-platelet therapy (APT)), Causal, Probable
- Serious adverse events related to Intervention (Procedure, APT)- Causal, Probable
- Adverse device effects (Non-SAE Related to Study Device- causal, probable)
- Serious adverse device effects (SAE Related to Study Device-causal, probable)
- Unanticipated serious adverse device effects (USADE)/UADE
- Adverse events by severity (Mild, Moderate and Severe) related to Device, Procedure or APT (causal, probable)

PR-NV16099

Version C

14. Ethics

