Aneurysm Dome		Maximum horizontal diameter of the aneurysm.	
Aneurysm Neck		Opening of the aneurysm where it meets the parent vessel	
Aneurysm Occlusion		 According to the Raymond–Roy Scale¹: Class 1: Complete Occlusion – complete obliteration of the aneurysm. Class 2: Residual Neck – persistence of any portion of the original defect of the arterial wall as seen on any single projection, but without opacification of the aneurysmal sac. Class 3: Residual Aneurysm– any opacification of the aneurysmal sac. 	
Attempted Procedure		Any procedure where Pipeline [™] Vantage Embolization Device with Shield Technology [™] was attempted i.e., successful puncture at the arterial access site.	
Bleeding Complications per GUSTO		 Bleeding complications shall be adjudicated using the GUSTO bleeding criteria which includes categorizing all bleeding events into the following categories: Severe or Life-threatening: Intracerebral hemorrhage Resulting in substantial hemodynamic compromise requiring treatment Moderate: Requiring blood transfusion but not resulting in hemodynamic compromise Mild Bleeding that does not meet above criteria 	
Cerebral Infarction		Evidence of new ischemic changes (infarction) on imaging. Further characterized as:	

PR-NV16099	Version C	Page 13 of 144 Mectronic
		 Asymptomatic: no associated focal neurological deficit symptoms (i.e., Silent Infarctions) Symptomatic: focal neurological deficit
Contrast Induced Complications		symptoms lasting less than 24 hours Complications arising due to the use of contrast agent used for imaging requirements during study procedure(s).
Delayed Intra-Cranial Hemorrhage (IC	н)	Any intracranial hemorrhage occurring >30 days post- procedure
Device Deficiency (DD)		Inadequacy of a medical device with respect to its identity, quality, durability, reliability, safety or performance. (ISO 14155:2011 3.15) Note: Device deficiencies include malfunctions, use errors, and inadequate labeling.
Device Movement		Unintended Pipeline stent (braid) Movement (as observed/discerned on imaging) of the implanted device following deployment.
		Device movement will be further characterized by:
		 Timing: Intra-procedural: Observed during the study index procedure
		 Post-procedural: Observed at a follow-up time point
		 Foreshortening: Movement on either or both ends of the device in opposite direction towards the aneurysm neck.
		 Migration: Movement of device where both ends move in a single direction away from the aneurysm neck.

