- Pregnancy test (Pregnancy test (serum or urine) only required for females of childbearing potential. Females who are surgically sterile or post-menopausal are not required to take a pregnancy test). At the 2-year follow-up, pregnancy test is only required for female subjects of childbearing potential that are undergoing DSA imaging.
- Record protocol specified medications
- Record concomitant medications
- If aneurysm is not occluded at 1 year or subsequent follow-up visits (per core lab assessment), DSA must be performed at 2-year follow-up. If child bearing potential woman becomes pregnant during the study, subject may obtain MRA without contrast instead of DSA.
- mRS assessment to be carried out by a certified independent assessor at site

ADVANCE Clinica	I Investigation Plan		
PR-NV16099	Version C	Page 85 of 144	Medtronic

- Full neurological exam and assessment of aneurysm symptoms (new, worsened, improved, stable)
- Assessment of Adverse events of interest

9.9.5. 3-Year

At 3-year post-procedure (±56 days), the following study assessments shall be performed and recorded in the eCRFs:

- Pregnancy test (Pregnancy test (serum or urine) only required for females of childbearing potential. Females who are surgically sterile or post-menopausal are not required to take a pregnancy test). At the 3-year follow-up, pregnancy test is only required for female subjects of childbearing potential that are undergoing DSA imaging.
- Record protocol specified medications
- Record concomitant medications
- If aneurysm is not occluded at 1 year and subsequent follow-up visits (per core lab assessment), DSA must be performed at 3- year follow-up. Subjects with aneurysm occluded at 1 year and subsequent follow-up visits (per core lab assessment) to undergo DSA, if performed per standard of care; if DSA not collected per standard of care, subject must undergo CTA imaging. Under certain conditions, MRA imaging may be obtained instead of a DSA or CTA imaging e.g., subjects with iodine allergies, borderline renal function, pregnancy, or concerns over excessive radiation. The justification for using MRA over DSA or CTA should be captured in the case report form. Precaution: DSA or CTA imaging are preferred over MRA imaging due to the risk of reduced image quality (artifact) when attempting to visualize near or inside the implanted device with MRA imaging.
- mRS assessment to be carried out by a certified independent assessor at site

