9.9.6. Unscheduled Visits

At unscheduled follow-up visit (any visit to the study site that is performed between the planned followup visits) that occurs post-procedure through the 3-year visit, the following study assessments shall be performed and recorded in the eCRFs:

PR-NV16099

- Record protocol specified medications
- Record concomitant medications
- DSA imaging (collected if performed per standard of care)
- Imaging of the treated aneurysm using CTA/MRA (collected if conducted per standard of care)
- mRS (for stroke events, mRS should be performed at a minimum of 90 days post event) assessment to be carried out by a certified independent assessor at site
- NIHSS (For stroke events, NIHSS should be performed at the time of event and 24 hours after event)*
- Full neurological exam and assessment of aneurysm symptoms (new, worsened, improved, stable)
- Assessment of Adverse events of interest

*Note that for assessments not performed at study center, the medical charts need to be obtained and sent to Sponsor for CEC evaluation.

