Device related Events of Interest	Events representing complications of the non-fatal, serious or non-serious in nat Device Thrombosis Parent Artery (In-Stent) Stenosis Incomplete Occlusion (At follow-up Mechanical Device Failures (Device OIncomplete Open Failure to Open OPushwire Separation	ure: o i maging) e Deficiencies) including but not l issues	limited to:
 Loss of Device Integrity (fracture, fragmentation break) Device- Catheter Interaction (excessive friction, trackability Device Foreign Body Reaction (Toxicity, Granuloma) Device Movement Foreshortening (delayed) Migration 			
DAPT Related Events of Interests	Events representing complications of the fatal or non-fatal, serious or non-seriou Bleeding Complications (GUSTO) Mild Moderate Severe Thrombocytopenia/Thrombotic the Nose bleeds (epistaxis) Allergic reaction to medications into Generalized Headache Dizziness Anemia Abnormal Liver and/or kidney functions	us in nature: rombocytopenic purpura cluding angioedema	py. These include

Abdominal pain, 0 Nausea, 0 Vomiting 0 Indigestion 0 Gastritis/Gastric Ulcer 0 Dyspnea Fatigue Arrhythmias/ventricular pause(s) Note: For comprehensive potential risks associated with dual antiplatelet therapy, please refer to the most current labelling for the specific antiplatelet drug e.g., Aspirin, Clopidogrel, Prasugrel, Ticagrelor

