12.1. Clinical Events Committee

A CEC shall be comprised of a minimum of three (3) physicians knowledgeable in the appropriate disciplines and medical specialties pertinent to the disease state being evaluated in this clinical study and will be responsible for an independent, objective and consistent review of AEs.

Event level adjudications will be performed by a single CEC member for start and stop dates, seriousness, causality assessment, severity and outcomes for all adjudicable adverse events per CEC charter.

The CEC will independently adjudicate each subject to pre-specified Events Of Interest (EOI) which indude the primary endpoint, secondary safety endpoints, and pre-specified events of interest per **Section 10.1**.

The CEC can request additional source documentation and any potential imaging obtained in support of the adverse event to assist with adjudication.

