13.3. Analysis Populations

To ensure adequate representation patient with large and giant aneurysms must be enrolled. All primary and secondary endpoints will be analyzed both on an ITT and PP basis. All summarizations and tabulations will be conducted on the ITT population, defined below.

Intent-To-Treat Population: All subjects who were consented and in whom deployment of the Pipeline[™] Vantage Device was attempted (i.e., puncture at the arterial access site), independent of the procedure being completed successfully.

Subject will not be considered part of the ITT population if the puncture at the arterial access site for deployment of Pipeline[™] Vantage Device was not successful. If the puncture at the arterial access site for deployment of Pipeline[™] Vantage Device was successful, the subject will be considered part of the ITT population. Consented subjects who withdraw consent prior to undergoing the study procedure or are found not to meet the inclusion/exclusion criteria prior to undergoing the study procedure, will not be included in the ITT population.

The ITT population will be the primary population for all analyses.

PR-NV16099

The PP population defined below will be used for sensitivity analyses and to provide outcomes for subjects with observed data.

Per-Protocol Population: Per-protocol population is ITT subjects excluding the following subjects:

- Subjects with use of more than 1 treatment device (e.g., coils) other than Pipeline[™] Vantage device during index procedure
- Subjects with failed implantation of study device at index procedure
- Subjects assessed as mRS ≥3 at baseline by independent and certified assessors

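### Device-effect rates for years 1–2 use the ITT population although 2-year imaging is required only for non-occluded aneurysms, so silent device events can be undercounted there and shifted into years 2–3

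*Combined protocol and SAP*

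**What the plan says.** Section 13.8.4 (Adverse Events) states: "Tables to summarize the incidence rates will be created for each of the following groups: (At 1 year, 1- 2 years", and then adds years 2–3. The groups include serious and non-serious adverse device effects judged causal or probable. No denominator is given there. Section 13.3 supplies the general rule: "All summarizations and tabulations will be conducted on the ITT population, defined below".

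Section 10.1 lists, among device-related events of interest, "Device Thrombosis Parent Artery (In-Stent) Stenosis Incomplete Occlusion (At follow-up" imaging), and also device movement. The Glossary ties these events to imaging. Device thrombosis and parent artery stenosis are findings on follow-up imaging graded by symptoms, and stenosis has an explicit asymptomatic category. Device movement is "Unintended Pipeline stent (braid) Movement (as observed/discerned on imaging").

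The imaging schedule in section 9.9 differs by year:
- **1 year:** DSA for implanted subjects.
- **2 years:** "If aneurysm is not occluded at 1 year or subsequent follow-up visits (per core lab assessment), DSA must be performed at 2-year follow-up". No imaging is listed at this visit for occluded aneurysms.
- **3 years:** DSA is mandatory if the aneurysm is not occluded. For occluded aneurysms DSA is used if it is standard of care, and "if DSA not collected per standard of care, subject must undergo CTA imaging", with MRA allowed under stated conditions.
- **Unscheduled visits (9.9.6):** "DSA imaging (collected if performed per standard of care"), and likewise CTA or MRA.

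On dating, section 12.1 says "Event level adjudications will be performed by a single CEC member for start and stop dates". No rule covers a finding first seen after a gap in imaging.

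**The concern.** An interval incidence rate is interpretable only if events in that interval could be observed in the subjects who form the denominator. For silent device events in years 1–2 this fails for most of the ITT population, because occluded subjects have no scheduled image between the 1-year and 3-year visits. They add to the denominator but can add to the numerator only through other imaging. If a finding persists to the 3-year image and takes that date as its onset, it is counted in years 2–3.

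The year 1–2 rate would then be too low and the year 2–3 rate too high. A reader could take this for a late rise in stenosis, thrombosis or movement of a permanent implant when the underlying rate is constant. The secondary endpoints in 13.8.3 avoid the problem: the imaging-based ones (occlusion, recurrence) are set at 1 and 3 years only, while the 2-year results are for clinically detected outcomes. Only 13.8.4 asks for a year 1–2 figure that includes imaging-detected events.

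**Working it through.** The plan states no shortfall figure, so there is none to reproduce. The check asks how large the shortfall could be.

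**Inputs from the documents.** Share of aneurysms completely occluded at 1 year, f:
- SHIELD (4.2.7): 141/188 = 75.0%
- PFLEX (4.2.8): 37/47 = 78.7%
- PREMIER (4.2.5): 113/138 = 81.9%
- PUFs, large and giant aneurysms (4.2.2): 79/91 = 86.8%

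If occluded is read as completely occluded, required 2-year imaging covers 1 − f: 25.0, 21.3, 18.1 and 13.2 per 100 subjects.

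**Inputs not in the documents, so varied.**
- RR: yearly risk of a silent imaging-detected event in non-occluded relative to occluded aneurysms.
- q: share of such events in occluded aneurysms that are found by imaging outside the 2-year rule.

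**Formula.** Let h be the yearly risk in occluded aneurysms.
- True year 1–2 events per subject: f·h + (1 − f)·RR·h.
- Missed events per subject: f·h·(1 − q).
- Shortfall: u = f(1 − q) / [f + (1 − f)·RR].

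**Example.** For SHIELD with RR = 2 and q = 0.5: u = 0.75 × 0.5 / (0.75 + 0.25 × 2) = 0.375 / 1.25 = 30.0%.

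| RR | q | u at f = 75.0% (SHIELD) | u at f = 81.9% (PREMIER) | u at f = 86.8% (PUFs) |
|---|---|---|---|---|
| 1 | 0 | 75.0% | 81.9% | 86.8% |
| 2 | 0 | 60.0% | 69.3% | 76.7% |
| 3 | 0 | 50.0% | 60.1% | 68.7% |
| 5 | 0 | 37.5% | 47.5% | 56.8% |
| 1 | 0.5 | 37.5% | 40.9% | 43.4% |
| 2 | 0.5 | 30.0% | 34.7% | 38.3% |

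PFLEX lies between SHIELD and PREMIER. With RR = 1 and q = 0 the shortfall is simply f.

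**Carry-over to years 2–3.** Suppose true yearly rates are equal, every missed finding is still visible at 3 years, and each is dated at detection. Years 2–3 then show (1 + u) times their true count:
- RR = 1, q = 0: 1.75 (SHIELD), 1.82 (PREMIER), 1.87 (PUFs).
- RR = 2, q = 0.5: 1.30, 1.35, 1.38.

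The apparent ratio of years 2–3 to years 1–2 is (1 + u)/(1 − u):
- Worst case: 1.75/0.25 = 7.0 at SHIELD and 251/25 = 10.0 at PREMIER.
- RR = 2, q = 0.5: 1.30/0.70 = 1.9 and 1.347/0.653 = 2.1.

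**The case against.** **The percentage is not an estimate of error.** A reader might infer that year 1–2 device events will be understated by 75–87%, or that the table will show a 7- to 10-fold rise. The documents do not support either as an expected result. The percentage is the earlier studies' occlusion rate. It equals the shortfall only with equal risk in both groups and no other imaging, and the fold-rise also needs persistence to 3 years and dating at detection. This objection stands.

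**Incomplete occlusion hardly fits.** Cases persisting from year 1 fall under the mandatory 2-year DSA. Incomplete occlusion after complete occlusion is recurrence, and PREMIER, SHIELD, PFLEX and PUFs report none. Clinically significant movement is defined partly through incomplete occlusion, so a higher risk in non-occluded aneurysms is plausible there. This also stands, and the point is limited to stenosis, thrombosis and movement.

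**The planned rows are pooled.** Section 13.8.4 groups events by seriousness, severity and relatedness, with no row for stenosis, thrombosis or movement. Clinically detected events in the same rows dilute the distortion. This stands.

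**Other late results exist.** A reader might infer that this table is the only view of late complications. It is not: 13.8.3 reports occlusion and recurrence at 3 years and stroke outcomes at 2 and 3 years, and 13.1 provides dated listings. None of these, however, is a specified rate by period for late stenosis, thrombosis or movement.

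**Details are deferred.** The ITT denominator comes from the general rule in 13.3, and 13.1 leaves detail to a later SAP. That makes correction easy but does not remove the problem, since the intervals and the default population are already written.

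**Conclusion.** The concern holds in limited form. Following the plan as written, silent parent artery stenosis, device thrombosis and device movement in occluded subjects can be under-ascertained in years 1–2. If they persist and are dated at detection, they are counted in years 2–3.

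The size is unknown from the documents. For this subset of events the year 1–2 shortfall could reach about 75–87% in the worst case (equal risk in occluded and non-occluded aneurysms, no other imaging). It is about 30–60% under several milder settings, for example 30–35% with 75–82% occluded, doubled risk in non-occluded aneurysms, and half of the events in occluded aneurysms found by other imaging.

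The overall adverse-event rows are affected less than this. Symptomatic events, which would prompt unscheduled imaging, and persisting incomplete occlusion are largely unaffected. The 1-year primary endpoints are unaffected, because DSA is scheduled for implanted subjects at 1 year. The tables are descriptive and no hypothesis test depends on them. What is at risk is the reading of the time pattern of late silent device events.

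**What to change.** In section 13.8.4, or in the SAP that expands it:

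1. Keep the three planned intervals for clinically detected events.
2. Tabulate imaging-detected device events (parent artery stenosis, device thrombosis, device movement) separately, for year 1 and for one combined year 1–3 interval. Use as denominator the subjects with evaluable follow-up imaging of the device in that interval.
3. Show the number of subjects imaged in each yearly interval.
4. State that these events are dated at first detection.

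The combined interval is preferable to a year 1–2 rate among subjects with required 2-year imaging. That group would be only about 13–25 per 100 subjects, all non-occluded, and would represent the whole population only if RR = 1.

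The cost is SAP wording and one extra table, with no new imaging or data. The downside is that no separate year 1–2 rate is given for silent device events, which the imaging schedule cannot support for most subjects.
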